### 2.4 Justification for the design of the Investigation

The design of the study causes minimal influence on the clinical tract of the patient, since no supplementary study visits are required. In case of malfunctioning of the study lenses, minimal effort is required to restore the microscopic viewing system to the standard-of-care with neglectable impact on the surgery duration.

### 2.5 Expected Duration of the Investigation

The study duration will be from the start of the surgical procedure till the end of the surgical procedure.

The end of the Investigation will be notified by the investigator within 15 days of the end of the Investigation to the EC/CA.

## 3 Eligibility Criteria

### 3.1 Inclusion criteria

Participants eligible for inclusion in this Investigation have to meet **all** of the following criteria:

1. Voluntary written informed consent of the participant or their legally authorized representative has been obtained prior to any screening procedures
2. Patients that are scheduled for primary vitrectomy surgery to treat retinal detachment or macular disease (pucker, macular hole, vitreomacular traction).
3. Both vitrectomy-only and combined phaco-vitrectomy surgeries
4. General or local anesthesia, or combination
5. Patients aged  $\geq 18$  years

All participants that are considered for Investigation participation as per the above criteria, will be documented on the Screening Log, including Screen Failures.

### 3.2 Exclusion criteria

Participants eligible for this Investigation must **not** meet any of the following criteria:

1. Patients aged  $< 18$  years
2. Patient who do not have sufficient command of the Dutch language to read and understand the informed consent form
3. Any disorder, which in the investigator's opinion might jeopardise participant's safety or compliance with the CIP.
4. Repeat vitrectomy surgery

Participants who meet one or more of the above exclusion criteria **must not proceed** to be enrolled in the Investigation and will be identified on the Screening Log as Screen Failure.

## 4 Study Procedures

### 4.1 Participant consent and withdrawal of consent

The Investigation will be conducted only on the basis of prior informed consent by the participants and/or their legally authorized representative(s). As such, no Investigation-related procedures will be conducted prior to obtaining written informed consent from potential participants.

The process for obtaining and documenting initial and continued informed consent from potential participants will be conducted in accordance with ISO 14155:2020, applicable regulatory requirements and internal Standard Operating Procedures (SOPs).

All originally signed obtained Informed Consent Forms (ICFs) must be retained/archived in the ISF at the Participating Site and must not be destroyed (even when a scanned copy is available) before expiration of the legal archiving term as defined in the CIP section entitled "Archiving".

Participants may voluntarily withdraw consent to participate in the Investigation for any reason at any time. The participant's request to withdraw from the Investigation must always be respected without prejudice or consequence to further treatment. Consent withdrawal will be documented in the participant's medical record.

Study data and samples collected before withdrawal can be used in the study. No new study data or samples will be collected after withdrawal of the participant.

### 4.2 Selection of Participants / Recruitment

In our standard-of-care, patients are proposed to undergo vitrectomy surgery in the outpatient clinic. When

a patient agrees to be scheduled for surgery, he or she will be explained that we have an experimental surgical viewing system available that we'd like to use for the surgery, and that for this purpose, we want to collect the intraoperative data only.

The moment when the informed consent form for the RESIGHT Disposable study is handed to the patient, will be at the same time when the vitrectomy informed consent form is also given to the patient (as is done in standard-of-care in all our patients). In elective surgery (e.g. macular pucker or floaters), the surgery is usually planned on another day than the day of the informed consent. In urgent surgery (e.g. retinal detachment), the surgery is usually performed the same day or the day after. Also in case of urgent surgery, there is a window of several hours between the moment of consent to the surgery and the surgery itself, since these non-scheduled interventions are scheduled only following after the scheduled surgery list. Hence, also in urgent surgery, the patient will have sufficient time to read and sign the informed consent form of the study.

The clinical data that will be used for the study are not different from those obtained in the standard clinical path, which implicates that no extra or specific examinations need to be performed for this trial.

### 4.3 Randomization Procedure (if applicable)

Not Applicable. Two study arms will be created depending on the surgical indication.

### 4.4 Premature discontinuation

Participants may voluntarily discontinue from the Investigation treatment and/or prematurely end their participation in the Investigation for any reason at any time. In such case the Investigator must make a reasonable effort to contact the participant (e.g., via telephone, e-mail, letter) in order to document the primary reason for this decision.

The Investigator may also decide at any time during the course of the Investigation, to temporarily interrupt or permanently discontinue the treatment if it is deemed that continuation would be detrimental to, or not in the best interest of the participant.

Similarly, the Sponsor, EC or authorized regulatory authority can decide to halt or prematurely terminate the Investigation when new information becomes available whereby the rights, safety and well-being of participants can no longer be assured, when the integrity of the Investigation has been compromised, or when the scientific value of the Investigation becomes obsolete and/or unjustifiable. In case the Sponsor decides to temporarily halt or prematurely end the Investigation, or to close a Participating Site in case of major non-compliance and/or critical safety issues, the Sponsor will notify the concerned EC/CA within 15 days of early termination or temporary halt, providing a justification of the event. In the event that the sponsor has temporarily halted or early terminated the Investigation on safety grounds, the Sponsor will inform the EC/CA within 24 hours of the event. In absence of EUDAMED, local guidelines with regards to notifications and submissions to the concerned EC/CA will be followed.

Circumstances requiring premature treatment interruption or discontinuation of the Investigation, include but are not limited to:

- Safety concerns related to IMD or unacceptable intolerability
- Investigation participation while in violation of the inclusion and/or exclusion criteria

In any such case of early termination and/or treatment interruption/discontinuation, the Investigator will continue to closely monitor the participant's condition and ensure adequate medical care and follow-up. It is recommended that follow-up information will be collected as follows:

For participants whose status is unclear because they fail to appear for visits without stating an intention to discontinue or withdraw, the Investigator must make every effort to demonstrate "due diligence" by documenting in the source documents which steps have been taken to contact the participant to clarify their willingness and ability to continue their participation in the Investigation (e.g., dates of telephone calls, registered letters, etc.).

A participant should not be considered lost to follow-up until due diligence has been completed.

## 5 Investigational Medical Device (IMD)

Investigational Medical Device Name (& company brand)	CE mark (Y - N - NA)	Used within Indication (Y or N)	Manufacturer of the device
Single-use WIDE-ANGLE LENS from ZEISS	N	Y	Carl Zeiss Meditec AG
Single-use ULTRA WIDE-ANGLE LENS from ZEISS	N	Y	Carl Zeiss Meditec AG
Single-use MACULA LENS from ZEISS	N	Y	Carl Zeiss Meditec AG
Reusable 128D lens from ZEISS (yellow)	Y	Y	Carl Zeiss Meditec AG (ref 30AL128D)
Reusable 60D lens from ZEISS (green)	Y	Y	Carl Zeiss Meditec AG (ref 30AL60DM)
Vitrex disposable contact lens	Y	Y	BVI / Vitrex (ref .VL00.D01)

### 5.1 Intended use

The device is intended to be used during ophthalmic surgery.

### 5.2 Identification and description of the IMD

See Investigator Brochure

### 5.3 Instructions for use

See section IFU in Investigator Brochure

### 5.4 Device qualification and classification

The device is intended for retinal visualization during vitreoretinal surgery, similar to its already existing reusable counterparts. It is manufactured by Carl Zeiss Meditec AG and delivered pre-packaged and sterilized.

The device is non-active. Risk classification is low (Class Is) since there is no physical contact between the device and the patient.

### 5.5 Device Accountability

After delivery, the IMD will be stored at room-temperature (as prescribed by the manufacturer) and opened from its sterile packaging immediately prior to use.

In the hospital, there is a standard procedure for returning faulty products. This procedure will be followed, similar to the standard clinical path. The IMD (used or un-used) will be returned to the manufacturer after the clinical investigation is completed.

## 6 Safety reporting

### 6.1 Definitions

The definitions and reporting requirements adopted in this CIP are based on the MDR 2017/745, ISO 14155:2020 and the MDCG 2020-10/1 European guideline.

#### 6.1.1. Adverse Event (AE)

An AE is any untoward medical occurrence, unintended disease or injury or any untoward clinical signs (including an abnormal laboratory finding) in subjects, users or other persons, in the context of a clinical investigation, whether or not related to the investigational medical device. (MDR Article 2(57))

Note:

1. This definition includes events that are anticipated as well as unanticipated events.
2. This definition includes events occurring in the context of a clinical investigation related to the investigational device, the comparator or the procedures involved. For the purpose of safety reporting all activities related to the use of a medical device may be considered procedures.

#### 6.1.2. Serious Adverse Event (SAE)

A SAE is any adverse event that led to any of the following:

- a) death,
- b) serious deterioration in health of the subject, that resulted in any of the following:
  - life-threatening illness or injury,
  - permanent impairment of a body structure or a body function,
  - hospitalisation or prolongation of patient hospitalisation,
  - medical or surgical intervention to prevent life threatening illness or injury or permanent impairment to a body structure or a body function,
  - chronic disease,
- c) foetal distress, foetal death or a congenital physical or mental impairment or birth defect. (MDR Article 2(58))

Note: Planned hospitalization for pre-existing condition, or a procedure required by the CIP, without a serious deterioration in health, is not considered a serious adverse event.

#### 6.1.3. Adverse Device Effect (ADE)

An ADE is an adverse event related to the use of an investigational medical device.

Note 1: This includes any adverse event resulting from insufficiencies or inadequacies in the instructions for use, the deployment, the implantation, the installation, the operation, or any malfunction of the investigational medical device.

Note 2: This includes any event that is a result of a use error or intentional misuse of the investigational medical device.

#### 6.1.4. Serious Adverse Device Effect (SADE)

A SADE is an adverse device effect that has resulted in any of the consequences characteristic of a serious adverse event.

#### 6.1.5 Unanticipated Serious Adverse Device Effect (USADE)

An (USADE) is an effect which by its nature, incidence, severity or outcome has not been identified in the current risk assessment.

### 6.1.5. Device Deficiency (DD)

A DD is any inadequacy in the identity, quality, durability, reliability, safety or performance of an investigational device, including malfunction, use errors or inadequacy in information supplied by the manufacturer.

For DD reporting, only non-CE marked surgical components described in the investigator brochure are considered as IMD.

Specifically for this study, a faulty production of such lens could obscure the retinal visualization for the surgeon. However, this issue would be noticed by the surgeon at the very beginning of the surgery and the lens would be replaced by another disposable lens sample (or by a reusable lens).

## 6.2 Adverse Events that do not require reporting

In general, the following should not be reported as AEs:

- Pre-existing conditions, including those found as a result of screening (these should be reported as medical history or concomitant illness).
- Pre-planned procedures, unless the condition for which the procedure was planned has worsened from the first trial-related activity after the subject has signed the ICF.

The following events are commonly observed and are therefore not considered as AEs for the purpose of the Investigation: adverse events that are related to malfunctioning of (an)other surgical device than the surgical microscope or the disposable RESIGHT lenses, e.g. the vitrectomy device.

Although these events should not be reported to the Sponsor, these should be recorded in the patient's medical notes according to routine practice.

The following events are not to be considered as SAEs:

- Pre-planned hospitalisations, unless the condition for which the hospitalisation was planned has worsened from the first Investigation-related activity after the subject has signed the informed consent.
- Hospitalisation as part of a standard procedure for CIP therapy administration. However, hospitalisation or prolonged hospitalisation for a complication of therapy administration will be reported as an SAE.
- Hospitalisation or prolongation of hospitalisation for technical, practical, or social reasons, in absence of an AE.

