## CIP SYNOPSIS

Title of clinical Investigation («Investigation»)	Title: ZEISS RESIGHT Disposable Lenses evaluation study
CIP Short Title Acronym	RESIGHT Disposable
Sponsor name	<University Hospitals Leuven (UZ Leuven) or KU Leuven>
Coordinating Investigator	[name]
Contact Address CI	UZ Leuven, [name]
Contact Email CI	[contact]
Contact Phone CI	[contact]
SIN number	CIV-23-02-042213
Other public database number	not applicable
Principal Investigators and Participating Sites	not applicable
Medical condition or disease under investigation	-Macular pathology requiring surgery: macular pucker, macular hole, vitreomacular traction -Retinal detachment
Study rationale	See row below
Primary objective	To evaluate the intra-operative efficacy of a new intra-operative viewing device.
Secondary objective(s)	/
Clinical Investigation Design	Investigator-initiated, mono-center, academic, prospective, interventional case study
Endpoints	To determine the effectiveness of the device compared to the reusable RESIGHT lenses and Vitreq contact lens presently used as standard-of-care.
Sample Size	120 eyes in two cohorts (60 in each cohort)
IMD	Disposable RESIGHT lenses
Comparator device(s)	Reusable RESIGHT lenses and Vitreq contact lens
Maximum duration of treatment of a Participant	Total inclusion time of each patient is surgery time (from first incision till removal of vitrectomy cannulas)
Maximum duration of the Investigation	Total inclusion time of each patient is surgery time (from first incision till removal of vitrectomy cannulas)
Anticipate First Patient First Visit (FPFV)	Q1 2023
Anticipate Last Patient Last Visit (LPLV)	Q4 2023
Third Parties	Carl Zeiss Meditec AG, [name]; Grant

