### 1.1.3 Wide-angle retina viewing system

During posterior segment surgery (vitrectomy), viewing of the retina is required. For that purpose, an

additional optical system below the microscope is required.

These optical systems can be divided into two categories:

1) Contact lens systems

[figure not shown]
This lens type is placed on the corneal surface with some contact gel in between the cornea and the lens. Different lenses are being used, either with a convex surface for wide-angle viewing or with a flat (or concave) surface for high-magnification viewing. In the former lens type, an image inverter is required to generate an erect retina image for the surgeon.

Although the optical quality of these contact lenses is very good, there are several disadvantages:

- The continuous contact with the corneal surface may cause corneal lesions (epithelial defect), or cause corneal edema during prolonged surgery sometimes rendering retinal visualization impossible necessitating to discontinue the surgery.
- The lens must be kept in a horizontal position on the eye, which requires an experienced surgical assistant to stabilize the lens during surgery. In our center, the surgical assistance is performed by residents in training who rotate every 6 weeks. Hence, it is impossible to have a well-trained surgical assistant for this purpose.
- When using a wide-angle viewing lens, although an extreme wide-field angle can be obtained, this field-of view is highly limited by the pupil size. Since vitrectomy surgery is usually performed in patients >65 years of age, the pupil dilation is often limited, restricting the field-of view.

As a result, the use of a contact lens during vitrectomy surgery is only occasionally used during surgery.

[figure not shown]

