#### 6.5.1 Sponsor's reporting of Serious Adverse Events and Device Deficiencies

The Sponsor is responsible to report to the CA's where the Investigation has commenced:

- Any SAE that has a **causal** relationship with the IMD, the comparator or the investigation procedure or where such causal relationship is reasonably possible;
- Any DD that might have led to a SAE if:
  - a) Appropriate action had not been taken, or
  - b) Intervention had not occurred, or
  - c) If circumstances had been less fortunate;
- New findings/update in relation to already reportable events.

These 'reportable events' must be reported within the following timelines:

- A reportable event which results in imminent risk of death, serious injury, or serious illness that requires prompt remedial action for other patients/subjects, users or other persons or a new finding to it must be reported immediately, but not later than **2 calendar days** after awareness by the Sponsor of a new reportable event or of new information in relation with an already reported event.
- Any other reportable event or a new finding/update to it must be reported immediately, but not later than **7 calendar days** following the date of awareness by the Sponsor of the new reportable event or of new information in relation with an already reported event.

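### Section 6.2, read literally, drops malfunction-related events of the comparator Vitreq contact lens, and arguably of the reusable RESIGHT lenses, from adverse-event reporting, in conflict with 6.1.1, 6.3.1 and 6.5.1

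*Combined protocol and SAP*

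**What the plan says.** The synopsis names the comparators as the "reusable RESIGHT lenses and Vitreq contact lens". Section 6.1.1, Note 2, extends the AE definition to "events occurring in the context of a clinical investigation related to the investigational device, the comparator or the procedures involved". The causality scale in 6.3.1 refers to the comparator as well as the investigational device. Section 6.5.1 requires the Sponsor to report to the competent authority any SAE with a causal "relationship with the IMD, the comparator or the investigation procedure", or where such a link is reasonably possible.

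Section 6.2 then lists events that are not AEs for this trial: "adverse events that are related to malfunctioning of (an)other surgical device than the surgical microscope or the disposable RESIGHT lenses". The one example given is the vitrectomy device. Of the events it lists, the section says: "Although these events should not be reported to the Sponsor". They are recorded only in the patient's medical notes.

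**The concern.** The 6.2 exclusion is defined by what it leaves out. Every surgical device is covered except the two named, and the comparator lenses are not named. Site staff who apply 6.2 as worded would withhold an event that the definitions count as an AE and that, if serious, the Sponsor must pass to the authority.

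What is at stake is the completeness of safety reporting for one class of event: those arising from malfunction of a comparator lens. For such an event the site and the Sponsor would be working under incompatible instructions. A descriptive statement about malfunction-related events by lens would also be uneven, because these events are reportable for the disposable lenses and set aside for at least one comparator.

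**Working it through.** No sample size, power or error rate is involved and the plan gives no figure to reproduce. The check is a comparison of the rules.

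**Step 1: classify each kind of event.**

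| Event | Under 6.2 | Under 6.1.1 and 6.3.1 | Under 6.5.1, if serious and causally related |
|---|---|---|---|
| Malfunction of a disposable RESIGHT lens | Kept (named exception) | AE | Reportable |
| Malfunction of the Vitreq contact lens | Excluded | AE (comparator) | Reportable |
| Malfunction of a reusable RESIGHT lens | Excluded on the wording; kept if the lens counts as part of the microscope | AE (comparator) | Reportable |
| Harm from normal use of a comparator, no malfunction | Not touched | AE (comparator) | Reportable |

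The second row is a plain contradiction. The third is a contradiction on one of two possible readings. The first and last rows are consistent.

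**Step 2: does the conflict matter for serious events?** Section 6.1.2 opens: "A SAE is any adverse event that led to any of the following". Being an AE is therefore a precondition for being an SAE. If 6.2 takes the event out of the AE class, it cannot enter the SAE class, and the duty in 6.5.1 has nothing to act on. The 2-day and 7-day limits in 6.5.1 run from the Sponsor's awareness, so an event that is never sent need not start either clock.

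**Step 3: does another rule restore the event?**
- Section 6.3.2 asks for all AEs, SAEs and DDs with no exemption for comparators, but it presupposes that the event is an AE.
- The Device Deficiency section of 6.1 limits deficiency reporting to components without a CE mark. The table in section 5 marks the reusable lenses and the contact lens as CE-marked, so they have no deficiency route.
- Section 2.3 ties the deficiency form, and the (S)AE form for resulting events, to a disposable RESIGHT lens.
- Section 6.3.5 reports all deaths whatever the cause. This restores fatal events only.

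Apart from deaths, nothing restores a comparator-malfunction event.

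**Step 4: which eyes are exposed?** Section 2.2 uses the Vitreq lens for endpoint 1, in the macular cohort only: up to 60 eyes. Endpoints 6 and 7 compare against the reusable lenses in both cohorts: up to 60 + 60 = 120 eyes. These are counts of exposed eyes, not of events.

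**The case against.** **The intent is ancillary equipment.** The only example in 6.2 is the vitrectomy device, the reason given is that such events are common, and the comparators are never mentioned. This is probably an oversight in drafting. That stands as an explanation, but the rule as worded covers every device outside its two exceptions, and staff have only the wording to apply.

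**The reusable lenses may belong to the microscope.** Section 1.1, on the surgical microscope, covers the RESIGHT system and describes it as closely integrated with the microscope. Against this, 6.2 names the disposable lenses separately from the microscope, although they mount on the same RESIGHT arm. The point remains open for the reusable lenses. It does not help for the Vitreq lens, which rests on the cornea.

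**There are partial safeguards.** Excluded events still go in the medical notes, deaths are always reported, and the Coordinating Investigator carries both investigator and sponsor responsibilities in this single-centre trial. The Sponsor may well learn of a serious intra-operative event anyway. This makes a lost report less likely but leaves the rules in conflict. There is no DSMB (6.6), and 8.3 judges independent monitoring unnecessary, so neither would pick up an omission.

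**Two stronger readings are tempting and should be resisted.**

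First, section 1.1.3 says contact lenses "may cause corneal lesions (epithelial defect), or cause corneal edema during prolonged surgery", and a reader might infer that these injuries would go unreported. They would not. That section attributes them to continuous contact, which is normal use, and 6.2 excludes only malfunction. One could assume a contact-lens event rate p and compute 1 − (1 − p)^60, which for p = 2% is about 70%. That is the chance of any such event, not of a lost one. The relevant rate is p times the share due to malfunction, and the documents give neither. With p = 2% and assumed shares of 1%, 5% and 50%, the result is about 1%, 6% and 45%, so the answer is set almost entirely by the assumption.

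Second, a reader might infer that a safety comparison between lenses is invalidated. None is planned: all eight endpoints in 2.2 concern lens performance, and 7.2.1 is an efficacy analysis. The surgeon also toggles between lenses within one operation (2.1), so attributing an event to a lens would be difficult whatever 6.2 said.

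**Conclusion.** The contradiction is real and follows from the text alone. It is certain for malfunction-related events of the Vitreq contact lens. For the reusable RESIGHT lenses it depends on whether they count as part of the microscope. A serious, non-fatal event of this kind would be removed by 6.2 before the reporting duty in 6.5.1 could apply.

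Its reach is limited to malfunction-related comparator events. Normal-use harm stays reportable, no planned endpoint or test changes, and no probability of a missed event can be given. This is a wording error in a safety-reporting rule. It should be corrected because it decides which events reach the Sponsor and the authority, but it does not threaten the trial's efficacy results.

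**What to change.** Reconcile 6.1.1, 6.2 and 6.5.1 by limiting the 6.2 exclusion to devices that are neither investigational nor comparator. For example, the exception could read: *other than the surgical microscope, the disposable RESIGHT lenses, the reusable RESIGHT lenses and the Vitreq contact lens*. Naming the reusable lenses also settles whether they count as part of the microscope. The vitrectomy device and similar equipment stay excluded, as 6.2 appears to intend.

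No change to the AE form is requested, since its content (Appendix 6) is not shown. The cost is one sentence in the protocol and possibly a few more AE forms.
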